10.6.2 Secondary Endpoints Summaries

The following results will be summarized descriptively, using the FAS:

- Time to first asthma related event/censoring (in days) will be summarized descriptively by treatment group as well as by a Kaplan-Meier plot of the time to asthma related event curves of the two treatment groups. A statistical comparison between treatment groups will be accomplished with the log rank test, for which the test statistic and associated p-value will be provided. For exploratory reasons, annual asthma related event rate will also be summarized descriptively by treatment group. As above for the primary endpoint analysis, this summary is performed using the assessments for the occurrence of asthma related events based on programmatic derivations from raw data and using the results from applying baseline Definition 1 where applicable (see [Section 9.2](#)).
- FEV₁ (FEV₁ [L]) and FeNO (nitric oxide level [ppb]) results – summary statistics for observed as well as change from baseline values, by visit for each treatment group
- ACQ results (overall score – see [Section 6.2.4](#)) – summary statistics for observed as well as change from baseline values, by visit for each treatment group
- AQLQ(S)+12 results (4 domain scores and overall score - see [Section 6.2.5](#)) – summary statistics for observed as well as change from baseline values, by visit for each treatment group
- Mean symptom score (each symptom separately) and mean ASD score (see [Section 6.2.6.1](#)) – summary statistics for observed as well as change from baseline values, by week for each treatment group
- Mean daily number of SABA puffs/inhalations over 1-week period (see [Section 6.2.6.2](#)) – summary statistics for observed as well as change from baseline values, by week for each treatment group; the summary will present the results applying calculation of baseline values according to Definition 1 for mean daily number of SABA puffs/inhalations (see [Section 9.2](#))
- Mean peak flow rate (see [Section 6.2.6.2](#)) – summary statistics for observed as well as change from baseline values, by week for each treatment group; the summary will present the results applying calculation of baseline values according to Definition 1 for mean peak flow rate (see [Section 9.2](#))
- EQ-5D-5L results (VAS score – see [Section 6.2.7](#)) – summary statistics for observed as well as change from baseline values, by visit for each treatment group
- EQ-5D-5L results (each of the 5 dimensions – see [Section 6.2.7](#)) – the shift from baseline to each post-baseline visit will be presented by treatment group
- Patient and Clinician Global Impression Questionnaires (see [Section 6.2.8](#) and [Section 6.2.9](#))

- for numeric scores: summary statistics for observed as well as change from baseline values (change from baseline values only applicable for PGIS and CGIS), by visit for each treatment group;
- for categorical result for each question: number and percentage of subjects for each rating for each visit by treatment group

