6.1.1 Justification of Sample Size

The sample size in this study will be approximately 80 subjects, ie, 40 subjects per treatment arm, randomized in a 1:1 ratio.

The sample size estimate was based on the estimated proportions of subjects in the 2 treatment groups expected to have an asthma related event as defined by the primary endpoint. In a study of similar design with another asthma controller therapy, rates of 6% in the active group and 44% in the placebo group were observed [3]. If these estimates were used as is, then a study with 40 subjects per group would have over 95% power. Considering likely variations from the cited study, estimates of sample were assessed assuming a Type I error of 5% and the proportion of subjects with an asthma related event ranging from 30% to 50% in the placebo group and 5% to 8% in the active group. In the 20 such scenarios examined, only in the cases in which the difference between treatments gets below 23% does the power fall slightly below 80%. In the vast majority of cases examined the power is greater than 90%.

The overall event rate may be assessed in a blinded fashion when an adequate amount of subject followup has occurred. If this event rate is found to be much lower than assumed, a sample size reestimation may be performed.

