9 OVERALL STATISTICAL CONSIDERATIONS

9.1 General Conventions

Efficacy, safety, PK, PD, and immunogenicity variables will be summarized using descriptive statistics. Descriptive statistics for continuous data will include number of subjects (n), mean, SD, median, minimum, and maximum. Summaries of change from baseline variables will include only subjects who have both a baseline value and corresponding value at the time point of interest. Descriptive statistics for categorical data will include frequency and percentage. Data will be summarized by treatment group (AVTX-002 and placebo) and overall (where applicable).

Descriptive statistics for continuous data will be displayed with applicable decimal precision as follows in relation to the source data (N: number of decimals for source parameter value, with $0 \leq N \leq 3$):

- Number (n)
- Mean, Median: N + 1
- SD: N + 2
- Minimum, Maximum: N + 0

Statistical hypothesis testing is planned to be performed on only the primary endpoint (see [Section 10.6.1](#)).

Listings will be provided for all collected study data.

Although the protocol defines the first day of administration of study drug as Day 0 (Visit 2, Baseline), for datasets and the study results reporting, the first day of administration of study drug is defined as Day 1. All other study days will be computed relative to Day 1. The study day for a particular event or visit will be calculated as $Date_{event} - Date_{first\ dose} + 1$ (for event occurring on or after first dose), and $Date_{event} - Date_{first\ dose}$ (for events occurring prior to first dose). For concomitant medications, AEs, clinical laboratory and vital signs assessments, as well as efficacy, PK, and PD assessments which occurred or were performed on or after the date of last administration of study drug, the study day relative to last study drug dose will also be displayed, ie, $Day_{last} = Date_{event} - Date_{last\ dose}$. In case of missing or partial dates being recorded for an event, the study day will not be calculated and will appear as missing in the subject listings.

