10.6.1 Primary Endpoint Analysis

The primary endpoint analysis is performed using the assessments for the occurrence of asthma related events based on programmatic derivations from raw data.

The proportion of subjects who experience any asthma related event will be summarized by treatment group, also including the proportion of subjects who experience each of the 5 separate criteria for an asthma related event (as identified in [Section 6.2.1](#)). A subject who experienced multiple asthma related events will be counted once in each of the applicable criteria categories and once for having an asthma related event.

Summary statistics showing the number and percentage of subjects with and without asthma related events in each treatment group will be provided via a 2x2 table. Comparison of the proportions of subjects who had an asthma related event will be via a Wald Z-test (including and without continuity correction). The test statistic, its associated p-value and a 95% confidence interval for the treatment difference will also be provided.

The summary table and associated statistical analysis of the occurrence of asthma related events will be repeated for results obtained using each of the 4 baseline values for mean daily number of SABA puffs/inhalations and mean peak flow rate calculated according to Definitions 1 to 4 in [Section 9.2](#), for all subjects in the FAS. In addition, the results for occurrence of asthma related events using the baseline values for mean daily number of SABA puffs/inhalations and mean peak flow rate calculated according to Definition 1 in [Section 9.2](#), for subjects in the Per Protocol Analysis Set, will also be presented.

Figures (one per subject) will display the % change from baseline in peak flow rate and change from baseline in daily number of SABA puffs/inhalations over time. Baseline values calculated according to Definition 1 in [Section 9.2](#) will apply. Occurrence of the following will also be

indicated on the figure for each subject: administration of each dose of study drug, reduction of fluticasone dose, discontinuation of salmeterol and fluticasone, end of study participation. As part of the figure, information on subject disposition (whether the subject completed the study or reason for early discontinuation from the study) and whether any criteria for occurrence of an asthma related event were met, will also be displayed.

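### Time to first asthma related event is to be summarised by means and medians that mix event days with censoring days, no time-to-event estimate with a confidence interval is planned, and the added log-rank test conflicts with SAP 9.1.

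*SAP*

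**What the plan says.** SAP 6.2.1 builds a single time variable. For a subject with an event (censor = 0) it is the day the first event started. For a subject without one (censor = 1) it is the day of the last visit. SAP 10.6.2 then says: "Time to first asthma related event/censoring (in days) will be summarized descriptively by treatment group as well as by a Kaplan-Meier plot". SAP 9.1 fixes what a descriptive summary contains: "Descriptive statistics for continuous data will include number of subjects (n), mean, SD, median, minimum, and maximum". No split by censoring status is specified.

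The same bullet of 10.6.2 also plans:

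- a Kaplan-Meier plot of both arms;
- a test: "A statistical comparison between treatment groups will be accomplished with the log rank test", reported as a statistic and p-value;
- an annual event rate per arm, labelled exploratory, with no ratio and no interval.

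Neither document plans a hazard ratio, a Kaplan-Meier probability or quantile with an interval, or any other between-arm time-to-event estimate.

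On testing, SAP 9.1 says: "Statistical hypothesis testing is planned to be performed on only the primary endpoint". The SAP version history shows that the log-rank comparison came in with Final 3.0. Protocol 12.3.5 plans only descriptive statistics for efficacy variables other than the primary one, and SAP Section 8, which lists departures from the protocol, does not mention the log-rank test.

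**The concern.** In the pooled variable, a subject who leaves event-free at Day 28 counts exactly like a subject with an event at Day 28. A low mean can therefore reflect early events or early event-free departure, and the table does not say which.

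The design makes this more than a formality. A subject who stops early has the final procedures four weeks after the last dose (Protocol Table 1, footnote 2), so an event-free leaver after one dose is censored near Day 29 in SAP numbering. Events may come later than that, because background therapy is withdrawn in steps up to Day 42. An early event-free leaver can then pull the arm mean down further than an event does.

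This is the secondary endpoint closest to the primary one, and it is suited to using partial follow-up. As written it yields a summary table that is hard to interpret, a plot, and a p-value whose standing is undefined if the primary comparison fails.

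**Working it through.** **Inputs from the documents.** SAP 6.1.1 gives "40 subjects per treatment arm, randomized in a 1:1 ratio", and from the cited study "rates of 6% in the active group and 44% in the placebo group were observed". Follow-up ends at Day 99 in SAP numbering. SAP 10.6.1 says "a 95% confidence interval for the treatment difference will also be provided", so two-sided 5% is assumed. Neither document gives a dropout rate or the timing of events, so both are assumptions below.

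**The plan's own figure.** For 44% v 6% with 40 per arm, SE = √(0.44×0.56/40 + 0.06×0.94/40) = 0.0870. Power = Φ(0.38/0.0870 − 1.96) = 99.2%, or Φ(0.355/0.0870 − 1.96) = 98.3% with a continuity correction of 1/40. The stated power of over 95% reproduces, so the rates and sample size are used as they stand.

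**The median.** With 40 subjects, an arm's pooled median equals the end-of-study day if at least 21 complete event-free. With no dropout:

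- 44% event rate: P(Bin(40, 0.56) ≥ 21) = 0.73
- 30% event rate: P(Bin(40, 0.70) ≥ 21) = 0.99
- 6% or 8% event rate: about 1.00

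So the medians tie at end of study in about 73% of trials at 6% v 44%, and about 99% at 8% v 30%. If event-free dropout of 10% or 20% is assumed, independent of events, the 0.73 becomes P(Bin(40, 0.504) ≥ 21) = 0.46 or P(Bin(40, 0.448) ≥ 21) = 0.21. The median then moves partly because of dropout.

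**The mean, worked example.** Active: 2 events at Day 60, 10 event-free leavers at Day 28, 28 reach Day 99. Placebo: 18 events at Day 60, 22 reach Day 99.

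- Pooled mean, active: (2×60 + 10×28 + 28×99)/40 = 3172/40 = 79.3 days
- Pooled mean, placebo: (18×60 + 22×99)/40 = 3258/40 = 81.45 days
- Pooled medians: 99 v 99
- Kaplan-Meier event-free: 28/30 = 0.933 v 22/40 = 0.550
- Difference 0.383. Greenwood SEs are 0.0455 and 0.0787, so the SE of the difference is 0.0909 and the 95% CI is 0.205 to 0.561
- Log-rank: 2 observed v 20×30/70 = 8.57 expected on active, variance 3.55, z = −3.49, p = 0.0005

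The pooled mean puts placebo ahead by 2.2 days, although active is clearly better.

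**How much dropout this takes.** With d active leavers at Day 28 and none on placebo, the active mean is (3882 − 71d)/40. It falls below 81.45 when d > 624/71 = 8.8, that is, 9 of 40. With 5 active leavers it is 88.2 v 81.45, the right order. With 10 leavers in both arms it is 79.3 v (18×60 + 10×28 + 12×99)/40 = 63.7, again the right order. Later events lower the threshold: with leavers at Day 29, it is 13, 10, 7 or 4 of 40 for events at Day 43, 57, 70 or 85.

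**How often.** Simulated chance (20,000 replicates) that the pooled mean favours placebo although active is truly better, over hazards starting at Day 0, 14 or 42:

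| Event rates | Equal dropout, 0–20% | 20% active v 10% placebo | 30% v 10% |
|---|---|---|---|
| 6% v 44% | 0–3.7% | 1.8–14.4% | 11–50% |
| 8% v 30% | 0.9–16% | 19–44% | 49–81% |

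**The log-rank test.** Simulated under no effect (6,000 trials per setting; event rate 25% or 44%, 0 or 15% dropout), the chance that the primary or the log-rank test is significant was 5.1–5.5% with the corrected primary test, against 3.0–3.4% for that test alone. With the uncorrected test it was 5.7–6.6%, against 5.2–5.6%. The addition is about two points and up to one point respectively.

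**The case against.** A reader might infer that the analysis would report the arms the wrong way round. The documents do not support that. The Kaplan-Meier plot and log-rank test in the same bullet account for censoring, and SAP 10.6.1 already gives the number with and without events and a risk difference with a 95% interval.

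The annual rate also ranks the worked example correctly. Taking one event per subject and participation ending at the event, it is 365.25×2/3172 = 0.23 v 365.25×18/3258 = 2.02 per year. If subjects with events stayed to Day 99, it is 365.25×2/3250 = 0.22 v 365.25×18/3960 = 1.66. In the simulations at the two pairs of rates tabulated above, person-time rates misordered the arms in at most 0.8% of trials. So it would be wrong to say that the plot and p-value are the only usable outputs. The rate is, however, exploratory, counts all events and not just first events, and has no interval.

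A reader might also infer serious inflation of the type I error. The simulation shows a small effect, and 9.1 can be read as implying that the log-rank test is not confirmatory.

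Pooling is itself an inference: 6.2.1 defines a censoring flag, and a table split by that flag is not ruled out. It remains the plain reading, because 10.6.2 names event/censoring days as one item and no split is specified.

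Finally, a Cox model is a matter of choice. Proportional hazards is uncertain when background therapy is withdrawn at Days 14, 28 and 42. That objection stands, and it limits the hazard ratio to a supportive role.

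**Conclusion.** The point holds as a reporting and consistency fault. The specified summary treats censoring days as if they were event days, so its mean and median have no useful interpretation. No time-to-event estimate with an interval is planned. SAP 9.1 and 10.6.2 disagree on whether anything beyond the primary endpoint is tested; 9.1 appears not to have been updated when the log-rank test was added.

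The size is moderate. The primary analysis is untouched, and the direction of effect would be visible from other planned outputs. Misordering by the pooled mean is uncommon at the design rates with equal dropout (at most 3.7%). It becomes a real risk only with more event-free dropout on active, or with smaller effects. The added error from the log-rank test is about one to two percentage points. The reversal and tie figures rest on assumed dropout and event timing. The contradiction and the missing estimate rest on the text alone.

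**What to change.** In SAP 10.6.2, replace the pooled descriptive summary with the following:

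- Per arm: number of subjects with an event and number censored, Kaplan-Meier event-free probability at end of study with 95% CI, and quartiles of time to event where reached.
- Between arms: the difference in Kaplan-Meier event-free probability with 95% CI.
- Optionally, a Cox hazard ratio with 95% CI as supportive, with a note that proportional hazards is uncertain under stepwise withdrawal of background therapy.

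Keep the plot and the log-rank test. Amend 9.1 and 10.6.2 to say that the log-rank p-value is nominal and supports no efficacy claim if the primary comparison fails. List the log-rank test in Section 8 as a change from the protocol.

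The cost is SAP wording and one revised table. No new data are needed.

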10.6.3 Exploratory Endpoint Analyses

The primary efficacy analysis (see [Section 10.6.1](#)) will be repeated for subjects in the FAS, for the subgroup of subjects with < 150 eosinophils/ μ L at the baseline visit. When evaluating SABA use and peak flow for this analysis, mean daily number of SABA puffs/inhalations and mean peak flow rate will be calculated according to baseline Definition 1 in [Section 9.2](#).

In addition, the primary efficacy analysis (see [Section 10.6.1](#)) will be repeated for subjects who experience an asthma related event in the period of time from date of first administration of study drug through 28 days after final dose of study drug. When evaluating SABA use and peak flow for this analysis, mean daily number of SABA puffs/inhalations and mean peak flow rate will be calculated according to baseline Definition 1 in [Section 9.2](#).

10.6.4 Interim Analysis

No formal interim analysis is planned for this study.

10.7 Safety and Tolerability

Safety analyses will be conducted using data from the SAS (as defined in [Section 7.1.2](#)). Safety variables will include TEAEs, clinical laboratory values, vital signs, and ECG results. No formal inferential analyses will be conducted for any safety variables, unless otherwise noted.

10.7.1 Adverse Events

All AEs are collected from the time that the informed consent is signed until the end of study.

The definition for an AE to be considered treatmentemergent is as follows:

- If AE start time is recorded: an AE will be considered treatmentemergent if it occurs on or after the time of first dose of investigational product and within 28 days after a subject's last dose of investigational product.
- If AE start time is not recorded: an AE will be considered treatmentemergent if it occurs on or after the date of first dose of investigational product and within 28 days after a subject's last dose of investigational product.

Additionally, an AE that occurred prior to the date of first study drug dosing and increased in severity after start of first dosing and within 28 days of a subject's last dose of investigational product will also be considered treatment-emergent. An AE that occurred prior to first study drug dose and then again after first study drug dose at the same severity is NOT considered treatment-emergent.

AE verbatim terms will be coded to a SOC and PT using MedDRA, version 24, 01 Sep 2021.

For incidence of AEs by treatment group, SOC and PT, a subject will be counted only once per SOC and PT.

For AE incidence presented as the number and percentage of subjects with a specific AE, if there is more than one occurrence of an event, the event with the worst severity or the highest rated causality category will be summarized.

Summaries of AEs by SOC and PT will be sorted alphabetically for SOC, then by descending order of frequency of PT (for AVTX-002) within each SOC (then alphabetically for ties).

Summaries of AEs by PT will be sorted by descending order of frequency of PT (for AVTX-002), then alphabetically for ties.

Missing assessments of seriousness, intensity and relationship to study drug that have been queried and remain missing, will be treated 'worst case' for presentation filtering purposes as follows:

- Missing seriousness assessment: AE will be regarded as serious.
- Missing relationship to study drug: AE will be regarded probably related to study drug, except when start date is prior to first dose of study drug (in which case the AE will be regarded not related to study drug).
- Missing intensity assessment:
 - If subject has died, AE will be regarded Grade 5 intensity.
 - If subject has not died but subject had intervention indicated for the AE, AE will be regarded Grade 4 intensity.
 - If none of the previous conditions are met, AE will be regarded Grade 3 intensity.

The following subject listings will be provided, using the SAS:

- All AEs (including TEAEs and nonTEAEs)
- All serious AEs (including serious TEAEs and serious nonTEAEs)
- All AEs leading to death
- All AEs leading to discontinuation of study drug

An overall summary of AEs will be provided, containing the number and percentage of subjects by treatment group with:

- any AEs
- any serious AEs
- any TEAEs
- any study drug related TEAEs

- any TEAEs leading to study drug discontinuation
- any study drug related TEAEs leading to study drug discontinuation
- any TEAEs by maximum CTCAE grade (Grade 1, Grade 2, Grade 3, Grade 4, Grade 5)
- any serious TEAEs
- any study drug related serious TEAEs
- any TEAEs leading to death
- any serious TEAEs by maximum CTCAE grade (Grade 1, Grade 2, Grade 3, Grade 4, Grade 5)

The following summary tables will be provided by SOC and PT, by treatment group:

- Incidence of TEAEs
- Incidence of study drug related TEAEs
- Incidence of TEAEs leading to study drug discontinuation.
- Incidence of study drug related TEAEs leading to study drug discontinuation
- Incidence of TEAEs by maximum CTCAE grade (Grade 1, Grade 2, Grade 3, Grade 4, Grade 5)
- Incidence of serious AEs (only if incidence of serious AEs and serious TEAEs differs)
- Incidence of serious TEAEs
- Incidence of study drug related serious TEAEs
- Incidence of serious TEAEs by maximum CTCAE grade (Grade 1, Grade 2, Grade 3, Grade 4, Grade 5)

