Discontinue salmeterol													
Taper/discontinue fluticasone													

Abbreviations: ACQ=Asthma Control Questionnaire; ADA=anti-drug antibody; AQLQ(S)+12=Standardized Asthma Quality of Life Questionnaire for 12 years and older; ECG=electrocardiogram; European Quality of Life – 5 Dimension 5 Level; Questionnaire ET=early termination; FeNO=fractional exhaled nitric oxide; FEV1=forced expiratory volume in 1 second; LIGHT= Lymphotoxin like, exhibits Inducible expression, and competes with Herpes Virus Glycoprotein D for Herpesvirus Entry Mediator.

1. Documentation of eligibility on all Inclusion and Exclusion Criteria is required before a subject can enter the study 30-day run-in period prior to Visit 2 (Randomization) when the subject is switched to stand alone Salmeterol and Fluticasone. Confirmation of eligibility should take place within a reasonable amount of time after the Screening Visit. If confirmation of eligibility is not available within 14 days from the date of Screening, the study Sponsor should provide approval for the subject to continue.
2. If a subject discontinues from the study/study drug, the Visit 9/ET procedures will be performed 4 weeks post last dose (±3 days).
3. A subject must be dosed with the Visit 7 (Week 8) dose no later than Day 56.
4. After Visit 2 (Day 0), visits should be scheduled relative to Visit 2 (Day 0). Visit 7 (Week 8) must not be performed later than Day 56.
5. Baseline visit to occur the day following completion of the 30-day run-in period with a window of an additional 3 days.
6. Visit 1a (Day -7) may be completed either by telephone or may be completed as an in-clinic visit, depending on the needs of the site and/or each individual subject. Visit 1a should occur with 7 days remaining in the 30-Day Run-In (-2 Day window for Visit 1a). During this phone call/onsite visit, the subject should be reminded to begin daily peak flow testing, and daily completion of their diary to capture asthma symptoms, SABA use and daily peak flow values.
7. At Visit 2 (Day 0), Visit 5 (Day 28), and Visit 7 (Day 56), pre- and post-dose vital signs will be measured: Pre-dose vital signs should be taken within 60 minutes before dosing. Post-dose vital signs should be taken at least 60 minutes after dosing, prior to discharge.
8. Height will only be recorded at the Screening Visit.

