## 10.1 Study Duration

AVTX-002 and placebo treatment will be administered at Visit 2 (Day 0), Visit 5 (Day 28), and Visit 7 (Day 56). **A subject may not be dosed after Day 56.** The duration of the treatment period is considered 84 days, with each dose of study drug considered to be 28 days of treatment. The overall study period is approximately 135 days, including Screening and the 30-day, stabledose, run-in period.

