### **11 ADVERSE EVENTS**

#### **11.1 Definition of Adverse Events, Period of Observation, Recording of Adverse Events**

##### **11.1.1 Adverse Event Collection**

An AE is defined as any untoward medical occurrence in a patient or clinical investigation subject administered a pharmaceutical product that does not necessarily have a causal relationship with the product. An AE can therefore be any unfavorable and unintended sign (including a new, clinically important abnormal laboratory finding), symptom, or disease, temporally associated with the product, whether related to the product. An AE will be considered treatment-emergent if it occurs after the first dose of investigational product and within 28 days of a subject's last dose of investigational product. Additionally, an AE that occurred prior to dosing with study medication and increased in severity after start of dosing and within 28 days of a subject's last dose of investigational product will also be considered treatment emergent.

All AEs are collected from the time of the informed consent is signed until the end of study (Day 98/ET). This includes events occurring regardless of whether investigational product is administered. Note: Clinically significant observations noted during screening procedures (labs, physical examination, vital signs, etc.) should be entered as medical history. Only if the clinically

significant observation is clearly related to the performance of a screening procedure should it be entered as an AE (e.g., a hematoma because of drawing blood for screening labs). Where possible, a diagnosis rather than a list of symptoms should be recorded. If a diagnosis has not been made, then each symptom should be listed individually.

All AEs must be followed to closure, regardless of whether the subject is still participating in the study. Closure indicates that an outcome is reached or stabilization achieved (i.e. the investigator does not expect any further improvement or worsening of the event). When appropriate, medical tests and examinations are performed so that resolution of an event(s) can be documented.

Events that meet the protocol definition of an asthma related event are captured as part of the primary efficacy endpoint for the study, and therefore need not be recorded as an AE unless they meet the definition of an SAE. Asthma exacerbations that do not meet the protocol definition of an asthma related event should be captured as AEs.

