10.5 Treatment Exposure

Based upon the PK of the study drug (halflife of 18.0 to 27.0 days) and dosage administered, each dose will count as 28 days of exposure to study drug. Therefore, days of exposure to study drug will be calculated as:

$$(last\ study\ drug\ dose\ date - first\ study\ drug\ dose\ date) + 28$$

A subject listing of treatment exposure will be presented, using the SAS, including the date and time of each study drug administration, reason for a dose not administered, location of each injection for each study drug administration, confirmation whether the injections were administered 4-10 cm from the umbilicus (with reason if not), and whether the complete dose was administered (with reason if not). The study drug exposure (days) will also be included in the listing.

Exposure to study drug (days) will be summarized by treatment group and overall using descriptive statistics, for the SAS. The number and percentage of subjects receiving 3, 2, 1, and 0 doses of study drug, respectively, will also be presented.

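### Non-serious adverse events that start in the last 14 days of a completer's follow-up enter no SOC/PT, grade or relatedness table, although they are collected, fall within the Week 14 safety endpoint and arise while drug remains

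*SAP*

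**What the plan says.** Protocol 11.1.1 sets the rule: "An AE will be considered treatment-emergent if it occurs after the first dose of investigational product and within 28 days of a subject's last dose". A pre-dose AE that worsens within the same limits also qualifies. Protocol 12.3.4.1 repeats the 28 days. SAP Section 8 item 2 and SAP 10.7.1 keep the same limit, "within 28 days after a subject's last dose of investigational product", and change only how the start of the window is judged when no onset time is recorded.

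On the last dose, the notes to the Protocol's Table 1 say: "A subject must be dosed with the Visit 7 (Week 8) dose no later than Day 56". AE collection runs longer than the window. Protocol 11.1.1 reads "All AEs are collected from the time of the informed consent is signed until the end of study (Day 98/ET"). Protocol 7.2.2 places the secondary safety endpoint at visits up to Week 14, which Table 1 equates with Day 98.

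On exposure, SAP 10.5 cites the drug's pharmacokinetics ("halflife of 18.0 to 27.0 days") and on that basis credits every dose with 28 exposure days. Protocol 10.1 has the matching statement: "The duration of the treatment period is considered 84 days, with each dose of study drug considered to be 28 days of treatment".

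SAP 10.7.1 restricts its SOC/PT, maximum-grade and relatedness tables to TEAEs. The one exception is a SOC/PT table of all serious AEs, produced only if its counts differ from those of serious TEAEs.

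**The concern.** Safety and tolerability is a secondary objective, and the reader of the report will judge it mainly from the TEAE tables. Those tables stop two weeks before AE collection and the stated endpoint do. At that point, on the SAP's own half-life, treated subjects still carry a substantial part of the last dose.

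Efficacy is handled the other way round. The primary analysis uses follow-up to Day 98, and the version cut at 28 days after the last dose is an exploratory repeat (SAP 10.6.3). For AEs, the 28-day cut is the only version tabulated by term, grade and relatedness. A non-serious AE on Day 90 that the investigator rates as probably related would not appear in any of those tables.

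**Working it through.** **The plan's own figure.** The SAP 10.5 formula is (last dose day − first dose day) + 28. With doses on Days 0 and 56 it gives (56 − 0) + 28 = 84 days, which reproduces the treatment period in Protocol 10.1. The TEAE window closes on the same day.

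**Time outside the window, for a completer.**
- Protocol numbering: the window ends at Day 56 + 28 = 84 and collection ends at Day 98, so Days 85 to 98 fall outside, 14 days.
- SAP reporting numbering (first dose = Day 1): the window ends at Day 57 + 28 = 85, so Days 86 to 99 fall outside.
- Share of post-dose time: 14/98 = 14.3%. Share of follow-up after the last dose: 14/42 = one third.
- With the visit windows in Table 1 (last dose Day 53 to 56, final visit Day 95 to 101), the gap runs from 95 − 84 = 11 days to 101 − 81 = 20 days.
- For early terminators, Table 1 says "the Visit 9/ET procedures will be performed 4 weeks post last dose (±3 days"), so at most about 3 days fall outside.

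**Drug remaining.** Input: "halflife of 18.0 to 27.0 days" (SAP 10.5). Assumption: first-order decay of the last dose, ignoring subcutaneous absorption. Fraction remaining = 0.5^(t / half-life).

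| Time after last dose | Half-life 18 d | Half-life 27 d |
|---|---|---|
| 28 days (window closes) | 0.5^(28/18) = 34.0% | 0.5^(28/27) = 48.7% |
| 42 days (Day 98) | 0.5^(42/18) = 19.8% | 0.5^(42/27) = 34.0% |

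The window is 28/27 = 1.04 to 28/18 = 1.56 half-lives long. Carry-over from the first two doses raises the amount. With r the 28-day fraction, r(1 + r + r²) gives about 50% (18 d) to 84% (27 d) of one dose's amount when the window closes.

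**Where an AE with onset after the window is counted (SAP 9.1 and 10.7.1).**

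| Late AE | Counted in | Not counted in |
|---|---|---|
| Non-serious | All-AE listing, with day relative to last dose; 'any AEs' row, which also counts pre-dose AEs | Every SOC/PT, maximum-grade and relatedness table |
| Serious | Listings; 'any serious AEs' row; the conditional SOC/PT table of serious AEs | Related-serious and serious-by-grade summaries |
| Fatal | As serious, plus the listing of AEs leading to death | Row for TEAEs leading to death |

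**Follow-up by arm in a longer window.** Completers have about 98 − 56 = 42 days after the last dose, early withdrawals about 28. Protocol 10.2.2.1 withdraws subjects who restart asthma therapy after an asthma related event. As a limiting illustration, suppose every subject with an event withdraws and has no follow-up beyond 28 days, and everyone else completes. At the planning rates in Protocol 12.1, the added time averages 14 × 0.92 = 12.9 to 14 × 0.95 = 13.3 days per subject on active. On placebo it averages 14 × 0.50 = 7.0 to 14 × 0.70 = 9.8 days.

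**The case against.** The strongest reply is that the 28 days are a protocol definition that fits the rest of the design. The treatment period is 84 days at 28 per dose, the early termination visit is four weeks after the last dose, and contraception and pregnancy reporting use the same 28 days. SAP 10.5 cites the half-life when it sets 28 days of exposure per dose, so it was considered. The window also gives completers and early withdrawals much the same time at risk after the last dose. All of this stands. A reader might infer that the SAP departs from the protocol, or that the definition must be replaced; the documents support neither. Nor does the half-life single out Day 98, since 20% to 34% of the last dose remains then, and a residual amount is not shown to equal a pharmacological effect.

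It also stands that late data are not lost from the report. A reader might infer that late AEs vanish from every table, but the two overall rows and the conditional serious-AE table contain them, and the listings show their day relative to the last dose. Laboratory and vital-sign summaries do not depend on the TEAE window. Tables of TEAEs leading to study drug discontinuation are essentially unaffected, because dosing ends by Day 56.

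What the reply does not answer is the missing tabulation. The 'any AEs' row mixes late events with those from consent and the run-in. The conditional table covers only serious events and may mix in pre-dose ones. Picking late non-serious AEs out of a listing is possible in about 80 subjects, but it gives no comparison by arm, term or grade.

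**Conclusion.** The point holds as a gap in tabulation. For subjects who receive the third dose and are followed to Day 98, non-serious AEs starting in the final 14 days enter no SOC/PT, maximum-grade or relatedness table. Late serious AEs are covered in part. The gap is about 14% of a completer's post-dose person-time (11 to 20 days once visit windows are allowed for) and close to nil for early terminators.

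It is tempting to read that as 14% of AEs missing from the tables. The documents do not support this. It would need a constant AE rate, and subjects count once per SOC and PT, so a late recurrence of an earlier term removes nothing. The share of table entries lost is not known.

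The 34% to 49% residual rests on the SAP's half-life range and simple first-order decay of the last dose; carry-over from earlier doses would raise it. One minor exception: an AE with a wholly missing start date is treated as a TEAE (SAP Table 3).

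**What to change.** In SAP 10.7.1, keep the protocol's 28-day TEAE tables. Add overview rows and SOC/PT, maximum-grade and relatedness tables for all AEs with onset or worsening from first dose through the end-of-study or early termination visit, including the serious, related-serious and fatal summaries. Record the addition in SAP Section 8.

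Beside these tables, show person-time or exposure-adjusted incidence by arm, because follow-up after the last dose differs between completers and early withdrawals and may therefore differ by arm.

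The cost is SAP wording, one more analysis flag and a few extra tables. No new data are needed and the protocol's definition is unchanged. The downside is unequal follow-up in the longer window, which the person-time display makes visible but does not remove.
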